#### 6.1.1. Analysis Populations

All data presentations will be based the intent-to-treat (ITT) population, which includes all randomized patients.

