The same MMRM, ANOVA and ANCOVA models excluding treatment effect will be used to present data for Study Period III, where appropriate.

Unless otherwise specified, for all analyses using the last-observation-carried forward (LOCF) approach in Study Period II, endpoint is defined as the last nonmissing observation obtained from Visit 3 through Visit 8; for the analyses using LOCF in Study Period III, endpoint is defined as the last nonmissing observation from Visit 9 through Visit 15.

In the analyses of some efficacy variables for Study Period II, the baseline-observation-carried-forward (BOCF) approach is considered. The BOCF endpoint is defined as follows:

For randomized patients who complete the treatment period (that is, complete the scheduled Visit 8) and have last nonmissing value at Visit 8, the BOCF endpoint is defined as the last nonmissing observation, for randomized patients who discontinue early (that is, do not complete the scheduled Visit 8) but with at least one non-missing baseline value, the BOCF endpoint is defined as the baseline value.

Categorical comparisons between treatment groups will be performed using Cochran-Mantel-Haenszel (CMH) test controlling for pooled investigative site and Fisher's exact test for Study Period II, when appropriate. For the categorical data, the number and percentage of patients for the categorical variables will be presented for Study Period III.

Where appropriate, variables will be summarized descriptively (frequency and percent will be summarized for categorical variables; number of patients with a non-missing observation, mean, SD, median, minimum, and maximum will be summarized for continuous variables) by study visit.

For those data summaries accompanied by individual patient data listings, data will be sorted by investigator ID, patient ID, and visit or event number if it is available.

Changes made to the data analysis methods will not necessarily require a protocol amendment and will be described in an updated SAP and reflected in the final report.

Statistical analysis of this study will be the responsibility of Eli Lilly and Company or designee. SAS® software will be used to perform most or all statistical analyses.

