
CAT)  f. 50% Response rate (MMRM-CAT)  g. Sustained response rate  h. Cumulative distribution of BPI average pain score reduction (BOCF)
	
e. Response at each post-baseline visit: at least 30% reduction from baseline.  f. Response at each post-baseline visit: at least 50% reduction from baseline.  g. Sustained response: at least 30% reduction from baseline to endpoint; with a 30% reduction from baseline at an earlier visit than the last visit, and remains at least 20% reduction from baseline in every visit in between, if there are any intervening visits (based on BPI average pain score). The sustained response analyses will include patients with both a baseline and at least two post-baseline values for BPI average pain score. h. The percentage of patients who have reached each threshold of BPI average pain reduction from baseline to BOCF endpoint (from >0% to 100% with a 10% increase) will be calculated. Discontinued patients will be considered as “no change”.
	
pooled investigative site for Study Period II.   For Variable 5.e and 5.f, the categorical, pseudo-likelihood-based repeated measures (MMRM-CAT) analysis will be used. See section 6.1.2 for details.   For Variable 5.h, the treatment group difference in the empirical cumulative distribution of the percentage pain reduction will be evaluated using Van der Waerden test for Study Period II.

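### Variable 5g drops patients with fewer than two post-baseline pain scores from the sustained-response denominator, although its own definition already makes them non-responders

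*SAP*

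**What the plan says.** Table HMGW.6.3, variable 5g, builds sustained response from two conditions on the BPI average pain score. The first is "Sustained response: at least 30% reduction from baseline to endpoint". The second is "with a 30% reduction from baseline at an earlier visit than the last visit", with at least a 20% reduction held at any visit in between. The same cell then sets the analysis set: "The sustained response analyses will include patients with both a baseline and at least two post-baseline values for BPI average pain score". The rate is compared between arms by Fisher's exact test and by a CMH test stratified by pooled site.

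Three other places bear on this:

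- **Population.** Section 6.1.1 states: "All data presentations will be based the intent-to-treat (ITT) population, which includes all randomized patients". Section 6.1.2 lets individual analyses specify otherwise. Table HMGW.6.1 sets the acute-phase efficacy population as patients with a baseline and at least one post-baseline observation.
- **Other response variables.** The LOCF response rates 5a and 5c have BOCF partners, 5b and 5d. Under Section 6.1.2, for a patient who discontinues early with a baseline on record, "the BOCF endpoint is defined as the baseline value", so that patient counts as a non-responder. In 5h, "Discontinued patients will be considered as" no change.
- **Time to sustained response.** Variable 6c right-censors patients without the event. Its row states no two-score restriction.

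**The concern.** For a patient with no score or one score, the definition of sustained response already gives the answer: non-responder. Nothing needs to be imputed. Removing the patient leaves the numerator unchanged and shrinks the denominator.

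Having a second score is an event after randomization, and treatment can affect it. Section 5.1 foresees both intolerance of the starting dose and discontinuation at Visit 3. If more patients leave one arm before a second score, that arm's rate gets the larger upward push, and the tests no longer compare the groups as randomized.

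The other BPI response rates have a planned version that treats dropout as failure, but 5g has none. The delta-based sensitivity analysis in Section 6.1.13.3 covers only the primary analysis. No planned output would therefore show how much the exclusion matters for sustained response.

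**Working it through.** **Can a patient with fewer than two scores respond?** In Section 6.1.2 the Study Period II LOCF endpoint is the last non-missing value ("endpoint is defined as the last nonmissing observation obtained from Visit 3 through Visit 8"). Variable 5g also needs a 30% reduction at an earlier visit, which I read as earlier than the visit supplying the endpoint. Two post-baseline scores are then the minimum, so every patient excluded by the two-score rule is a non-responder.

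**Who is excluded by what?** Let N be the patients randomized to an arm, all with a baseline score, m0 those with no post-baseline score, and m1 those with exactly one. Write m = m0 + m1, and r for the sustained responders.

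- All randomized: r / N
- General efficacy set (Table HMGW.6.1): r / (N − m0)
- Variable 5g: r / (N − m0 − m1)

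The step peculiar to 5g is the loss of m1.

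**Inputs.** Section 5.2 gives about 184 patients at 1:1, so N = 184 / 2 = 92 per arm. It gives about 81% completion, so about 0.19 × 92 = 17.5 dropouts per arm. The SAP gives no sustained-response rate, no analysis N for 5g and no early-dropout rate, so there is no planned figure to reproduce. All values of r and m below are assumptions.

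**Within one arm.** The inflation factor relative to all randomized is N / (N − m). With r = 35, the all-randomized rate is 35/92 = 38.0%.

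| m | 5g rate | factor |
|---|---|---|
| 2 | 35/90 = 38.9% | 1.02 |
| 5 | 35/87 = 40.2% | 1.06 |
| 9 | 35/83 = 42.2% | 1.11 |
| 17 | 35/75 = 46.7% | 1.23 |

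The last row is a ceiling: every expected dropout would have to leave before a second score. To separate the two steps, suppose m = 5 is made up of m0 = 2 and m1 = 3. The general efficacy set already gives 35/90 = 38.9%, and 5g's own step goes from there to 35/87 = 40.2%.

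**Between arms.** Assume an equal all-randomized rate of 35%, or 0.35 × 92 = 32.2 responders per arm. The 5g rate is 0.35 / (1 − excluded share).

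- 6% versus 3% excluded: 0.35/0.94 = 37.23% and 0.35/0.97 = 36.08%, a difference of 1.15, about 1.2 points.
- 8% versus 2% excluded: 0.35/0.92 = 38.04% and 0.35/0.98 = 35.71%, a difference of 2.33, about 2.3 points.

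For scale, the standard error of a difference between two 35% rates with 92 per arm is √(2 × 0.35 × 0.65 / 92) = 0.070, or 7.0 points. The two shifts are about 0.16 and 0.33 standard errors.

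If m is equal in both arms, a zero difference stays zero, and a non-zero difference is multiplied by N / (N − m).

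**The case against.** The strongest reply is that 5g is openly defined among evaluable patients, and that counting early leavers as failures is a choice of estimand. The set is indeed disclosed and reproducible, so it is not a contradiction. But the plan makes the other choice for 5b, 5d and 5h, and for 5g the definition itself already classifies the excluded patients.

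A second reply is that few patients are affected, and this is probably right. BPI average pain is due at every scheduled visit, since Table HMGW.6.2 lists a missing value as a significant deviation. Visit 3 comes after about one week. The same table allows at most 11 days after each of Visits 2 and 3, so the second score is due within 11 + 11 = 22 days. An early discontinuation visit may also supply one. The 1.23-fold ceiling has no support in the document as a likely case.

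A third is that 5b, 5d and 5h already show whether dropout drives response. They help, but none of them measures sustained response.

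A reader might infer more than the document supports:

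- **That 5g breaches the ITT population.** Section 6.1.1 does say "which includes all randomized patients", but Section 6.1.2 allows exceptions and Table HMGW.6.1 already requires one post-baseline value for efficacy. Patients with no score are not removed by 5g in particular.
- **That the treatment comparison is necessarily biased.** Higher rates in both arms are not in themselves a false difference. That requires unequal early loss, which the SAP neither states nor predicts.
- **That 6c carries the same exclusion.** The broad wording of the restriction leaves room for the question, but the row for 6c states no such rule.

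**Conclusion.** The point holds as a minor one. Variable 5g removes patients whom its own definition makes non-responders, and it is stricter than the general efficacy set by the patients with exactly one post-baseline score. The direction within each arm is certain: the rate cannot fall, and it rises if there are any responders and anyone is excluded.

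The effect on the Fisher and CMH comparison is conditional on very early dropout differing between arms. Its size is unknown. The 1.2 and 2.3 points rest on an assumed 35% rate and on assumed exclusions that combine patients with no score and patients with one, so they overstate what is due to 5g's extra rule alone. Variable 5g is one of many secondary variables without multiplicity adjustment, and the primary MMRM does not depend on it. The case for changing it is that the change is cheap and removes a possible bias.

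**What to change.** In Table HMGW.6.3, for 5g:

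1. Use as the denominator all randomized patients with a baseline BPI average pain score, and count those with fewer than two post-baseline scores as non-responders.
2. Keep the present two-score set as a supportive analysis, and report by arm how many patients it excludes, split into no score and exactly one.
3. State that the two-score restriction does not apply to 6c, where patients without the event are already censored.

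This takes a sentence or two and no new data. The reported sustained-response rates will be slightly lower.

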### 6.1.13.3. Sensitivity Analysis

To assess the possible impact of missing data on the primary efficacy analysis conclusions, a sensitivity analysis will be performed leveraging a delta based approach. The approach for this analysis is to vary the assumptions of missing data for the primary analysis in a systematic way. Basically, the method will be to predict the missing outcomes and then add a value ( $\Delta$ ) to the predictions in the duloxetine treatment group consistent with the sensitivity approach suggested in Permutt (2015). This procedure will be repeated multiple times for different values of  $\Delta$  using the following steps:

- 1) Predict the missing outcomes for each treatment via multiple imputation based on observed primary endpoint and baseline values. Such imputation will be carried out using a Markov Chain Monte Carlo method with a Jeffreys prior via SAS® PROC MI. Thirty (30) such imputations will be created.
- 2) Add the corresponding  $\Delta$  value to the imputed duloxetine treatment values.
- 3) Conduct the primary analysis separately for each of the 30 imputations.
- 4) Combine the results of these analyses using Rubin's combining rules, as implemented in SAS® PROC MI ANALYZE.

The above steps will be repeated multiple times for different values of  $\Delta$  with  $\Delta$  ranging from (0, twice the observed treatment effect seen in the primary analysis). For example, if the overall mean change from baseline for placebo is -3.6 and the maximum overall treatment difference is -1.5, then  $\Delta$  would range from (0,7.2).

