### 3. Revision History

SAP version 1 was approved on 10Feb2011, and SAP version 2 was approved on 11Dec2014 both before unblinding. The following changes were made to the SAP since the version 1:

- In Section 5.3, added patients could be re-screened based on revised protocol (b).
- The section of 'Determination of Sample Size' was moved to Section 5.2 and updated to reflect more accurate assumptions around dropout rate.
- More details of patient population, baseline and post-baseline definitions for all efficacy and safety analyses are summarized in Table HMGW.6.1.
- The details of definition of treatment group for Study Period II/III were added in Section 6.1.2, and analyses for Study Period II/III were added in Section 6.1.13 and 6.1.14.
- Removed the potential DLX\_NOIP treatment group for SP IV in Section 6.1.2.
- In Section 6.1.4, a selection model and a placebo multiple imputation (pMI) approach were added to handle dropouts or missing data.
- The details of definition of baseline concurrent/ongoing therapies were added in Section 6.1.8.
- The details of definition of significant protocol deviations were added in Section 6.1.9 and summarized in Table HMGW.6.2.
- More details of definition of last dose date for Study Period II and Study Period III were added in Section 6.1.10.
- More details of the test of maintenance of effect were added in Section 6.1.13.2 and Section 4.2.
- Added Section 6.1.13.3 for sensitivity analysis and updated the sensitivity analysis employed.
- More details of definition of treatment-emergent adverse events (TEAE) for Study Period II and Study Period III were added in Section 6.1.14.1.
- The details of definition of normal values at baseline were added for treatment emergent and potentially clinically significant analyses in vital signs and ECGs in Section 6.1.14.3 and 6.1.14.4 respectively.
- Analyses for non-suicidal self-injurious behavior were added in Section 6.1.14.5.
- Adjusted paragraph order in the safety Section 6.1.14.
- The details of American College of Rheumatology (ACR) criteria for fibromyalgia (Wolfe et al. 1990) were added in Section 6.3.2.

- The section of 'Changes in the Conduct of the Study or Planned Analyses' was removed since it will be summarized in the clinical study report for this study.
- Update the Interim Analysis in Section 6.2.
- Removed Appendix 1 Details of Sensitivity Analysis and Appendix 2 Implementation of Placebo Multiple Imputation.

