## **5.2. Determination of Sample Size**

Approximately 184 patients will be randomized in a 1:1 ratio to the duloxetine and placebo treatment groups. This study is to assess the difference of the mean change in BPI average pain severity from baseline to the last time point (Visit 8, Week 13) in Study Period II between treatment groups. Assuming that there will be some missing post-baseline data, and about 81% completion rate at acute phase by Visit 8 or Week 13, this sample size will provide at least 80% power to detect the treatment difference of 1.0 point with  $\alpha=.05$ . All the parameters used in the sample size calculations were based on the MMRM analysis of data from 3-month, placebo-controlled, acute treatment period in 2 adult FM studies: Study F1J-MC-HMCA and Study F1J-MC-HMCJ.

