#### **6.1.4. Handling of Dropouts or Missing Data**

Missing efficacy and safety data can occur for multiple reasons, including missed patient visits (for example, patients discontinuing from the study early) and scales or measures with missing item scores.

When change from baseline is assessed, only patients with a baseline and at least one post-baseline measurement will be included in the analyses.

For the repeated measures analyses, the model parameters are simultaneously estimated using restricted likelihood estimation incorporating all of the observed data.

Unless otherwise specified, when a total score or an average score is calculated from individual items, it will be considered missing if any of the individual items are missing.

For the assessment of efficacy, handling of missing data depends on the missing data mechanism assumptions. There are three missing data mechanisms: 1) missing completely at random (MCAR), 2) missing at random (MAR) and 3) missing not at random (MNAR). Three primary statistical approaches to handling missing data will be utilized: mixed model repeated measures (MMRM) analyses, ANCOVA/ANOVA using last observation carried forward (LOCF) change from baseline to endpoint, and ANCOVA/ANOVA using baseline observation carried forward (BOCF) change from baseline to endpoint. The LOCF and BOCF imputation methods in general make MNAR assumption, while the repeated measures analysis assumes MAR. A sensitivity analysis will be performed to assess the impact of missing data assumptions on the primary analysis conclusions (see section 6.1.13.3 for details).

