### 6.1.13. Efficacy Analyses

#### 6.1.13.1. Primary Outcome and Methodology

The primary objective of this study is to evaluate the efficacy of duloxetine 30/60 mg once daily compared with placebo on the reduction of average pain severity as measured by the BPI average pain severity rating during the Study Period II in adolescents with JPPFS.

The primary efficacy analysis will be the contrast between duloxetine and placebo at the last visit in Study Period II (Visit 8, Week 13) from a MMRM analysis on change from baseline in the BPI average pain score as described in Sections 6.1.2 and 6.1.3.

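### SAP Section 6.1.13.3 gives two upper limits for delta: its rule yields 3.0 for its own example, but the example prints 7.2

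*SAP*

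**What the plan says.** SAP Section 6.1.13.3 imputes missing outcomes in both arms, adds a value delta to the imputed duloxetine values only, repeats the primary analysis on each of 30 imputed data sets and combines the results by Rubin's rules. This is repeated for several values of delta.

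The range of delta runs from 0 to "twice the observed treatment effect seen in the primary analysis". The next sentence gives an example: "if the overall mean change from baseline for placebo is -3.6 and the maximum overall treatment difference is -1.5", in which case delta "would range from (0,7.2".

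The effect that the rule refers to is fixed in Section 6.1.13.1: "The primary efficacy analysis will be the contrast between duloxetine and placebo at the last visit in Study Period II (Visit 8, Week 13". Section 6.1.6 describes it in the same way.

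**The concern.** The rule and its example use different quantities. The rule refers to the between-arm contrast. The example's limit matches twice the placebo arm's change from baseline and leaves the stated difference of -1.5 unused. Two programmers could each follow this section and produce different ranges.

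The limit depends on observed results, so the formula is the only pre-specification of the range. If it stays ambiguous, the range will be chosen with unblinded results in view. This is also the only analysis in the SAP that varies the missing-data assumption systematically. A range that stops short of the point where the primary result loses significance would make that result look more robust than a wider range would.

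**Working it through.** **1. Reproducing the printed limit.** Inputs from the Section 6.1.13.3 example: placebo change -3.6, treatment difference -1.5 (so the implied duloxetine change is -5.1).

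| Candidate | Upper limit |
|---|---|
| Rule as written: 2 × 1.5 | 3.0 |
| 2 × placebo change: 2 × 3.6 | 7.2 |
| 2 × implied duloxetine change: 2 × 5.1 | 10.2 |
| 3.6 + 1.5 | 5.1 |
| 3.6 + 2 × 1.5 | 6.6 |
| 2 × 3.6 + 1.5 | 8.7 |

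Of these, only twice the placebo change gives 7.2. The printed limit is 7.2/3.0 = 2.4 times the rule's.

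**2. Whether the difference matters (illustration).** Inputs and assumptions:

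- 184 patients randomized 1:1 (Section 5.2), so 92 per arm.
- Completion: "about 81% completion rate at acute phase by Visit 8 or Week 13". I take p = 0.19 of duloxetine Week 13 values as missing, and assume imputed patients average the same as their arm at delta 0.
- Standard error: "this sample size will provide at least 80% power to detect the treatment difference of 1.0 point", at two-sided 0.05. At exactly 80% power, SE = 1.0/(1.960 + 0.842) = 0.357. This is the largest SE the planning statement allows; the realised SE could be larger.

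Adding D to the imputed duloxetine values moves the difference by pD towards placebo and adds some variance:

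z(D) = (effect − pD) / √(SE² + p(1−p)D²/92)

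For the example's effect of 1.5:

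- D = 3.0: (1.5 − 0.57)/√(0.1274 + 0.0151) = 0.93/0.377 = 2.46, p = 0.014.
- D = 7.2: (1.5 − 1.368)/√(0.1274 + 0.0867) = 0.132/0.463 = 0.29, p = 0.78.
- z = 1.96 at D ≈ 3.87.

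A limit of 3.0 stops before significance is lost; a limit of 7.2 goes past that point.

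**3. How far this depends on the assumptions.**

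- *Smaller SE.* At 90% power, SE = 1.0/(1.960 + 1.282) = 0.308. Then z = 2.80 at 3.0, significance is lost at about 4.24, and z = 0.31 at 7.2.
- *Larger SE.* At D = 3.0 the effect stays significant while √(SE² + 0.0151) is below 0.93/1.96 = 0.4745, that is, for SE up to about 0.46.
- *Size of effect.* With SE 0.357 and the example's placebo change, setting z = 1.96 at D = 2 × effect gives 1.17, and at D = 7.2 gives 2.27. The two limits lead to different findings for observed effects of about 1.2 to 2.3 points.
- *Missing share.* At effect 1.5 they differ for about 9% to 25% missing with SE fixed, or 10% to 24% with SE scaled by √(0.81/(1−p)).
- *Planning effect.* At 1.0 point and SE 0.357, significance is lost at D ≈ 1.5. The rule's limit is then 2.0 (z = 1.69), so both limits contain that point.

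**The case against.** The best answer is that a stated rule ordinarily governs an illustrative example, so the limit is twice the contrast and 7.2 is a slip. That is a fair default. But the example brings in the placebo mean change, which has no role under the rule, and its limit is exactly twice that figure. The author may have meant a placebo-based limit.

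The consequence is also conditional. Section 6.1.13.3 names neither a tipping point nor a significance criterion. The narrower range lies inside the wider one, so the dispute is only about how far the analysis extends. At the 1.0-point planning effect the choice does not change whether the point of lost significance is found. The upper end of the 1.2 to 2.3 window rests on the hypothetical placebo change of -3.6. All of this stands and limits the weight of the point.

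Other analyses bear on missing data: "The LOCF and BOCF imputation methods in general make MNAR assumption, while the repeated measures analysis assumes MAR", and Table HMGW.6.3 applies both carried-forward methods to BPI average pain. Each makes one fixed assumption, so neither replaces a graded check. Section 6.2 adds that the sensitivity analyses may not be performed after a futility stop.

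The Revision History notes "Removed Appendix 1 Details of Sensitivity Analysis and Appendix 2 Implementation of Placebo Multiple Imputation". Nothing shows that either appendix dealt with the range of delta, so I draw nothing from this beyond the fact that no appendix is now available to consult.

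Finally, the illustration is a simple approximation to a repeated-measures analysis. Section 6.2 also equates 150 patients with about 71% of planned enrollment, which implies about 150/0.71 = 211 patients rather than 184. With about 105 per arm and SE held at 0.357, z is 2.48 at 3.0 and 0.29 at 7.2, so the pattern is the same.

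**Conclusion.** The concern holds. The section contradicts itself: 3.0 under its rule against 7.2 in its example. That needs no assumption beyond reading the treatment effect as the primary contrast that Sections 6.1.6 and 6.1.13.1 define. The SAP does not show which limit was intended.

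The point should be fixed, but its reach is limited to the missing-data sensitivity analysis. The primary estimate, its test and the type I error rate are not affected. Under the illustrative assumptions (92 per arm, 19% missing, SE 0.357), the choice of limit decides whether the analysis reaches the point of lost significance for observed effects of roughly 1.2 to 2.3 points. It does not do so at the 1.0-point planning effect.

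**What to change.** Before the final unblinding, state one upper limit in absolute value: either twice the Week 13 treatment contrast, or twice the Week 13 placebo mean change. Rewrite the example to match. The example now speaks of overall changes without a time point, so the revised text should name Week 13 explicitly.

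Add that the report will give the delta at which significance is lost, or say that none was found within the range. Fixing the delta steps in advance, or increasing delta until significance is lost, would be a useful option but is not essential.

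The cost is one or two lines of SAP wording, with no effect on trial conduct, sample size or the primary analysis. The trade-off is that a wider range may show a loss of significance that the narrower one would not reach.
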